ШΤ	Investigator-initiated Trial
KLA	Klinik Arlesheim
LCT	Lüscher Colour Test
LDQ	Leuven Dyspepsia Questionnaire
NTM	Nottingham Test Meal
OTC	Over The Counter
PHQ-12	Patient Health Questionnaire 12-items, depression module
PI	Principal Investigator
RCT	Randomised Controlled Trial
RDQ	Reflux Disease Questionnaire
SAE	Serious Adverse Event
SDV	Source Data Verification
SOP	Standard Operating Procedure
SPC	Summary of product characteristics
SUSAR	Suspected Unexpected Serious Adverse Reaction
TMF	Trial Master File

STUDY SCHEDULE

Study Periods	Screening	Physiological Measurement and Treatment	Physiological Measurement and End
Visit	1	2	3
Time (days)	Ca14-28d	1	28±14d
Medical History and Demographics	x		
Leuven Dyspepsia Questionnaire (LDQ)	x		x
Screening questionnaires	x		
Pregnancy test (urine)	x	(x)	
In-/Exclusion Criteria	x		
Patient Information and Informed Consent	x		
Primary Outcome Measure: LDQ total score	x		x
Secondary Outcome Measure: other GI symptom questionnaires	x	x	x
Lüscher Colour Test	x	x	x
Physiological Measurement (13C BT, HRV)		x	x
Intake of the Study Medication (Amara Drops)		x	x
Compliance with therapy			x
Satisfaction with therapy / Whether a prescription of Amara is wanted			x
Concomitant Medication, Therapy	x	x	x
Serious Adverse Events	x	x	x

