4. STUDY OBJECTIVES

4.1 Overall Objective

The purpose of the present study is to evaluate whether the herbal drug Amara improves the subjective, perceived burden of abdominal symptoms in patients with functional dyspepsia. It will also assess if the treatment is well tolerated. The present study will also investigate psychological and physiological function. This additional information should provide insight into which patients benefit the most from the treatment with Amara. The results of this prospective, open-label therapeutic study will also inform the study design for any subsequent RCT study in functional dyspepsia.

4.2 **Primary Objective**

Document perceived changes in upper gastrointestinal, dyspeptic symptoms reported by patients with functional dyspepsia treated with Amara for 4 weeks, as assessed by the Leuven Dyspepsia Score between visit 1 (off treatment) and 3 (after treatment)..

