4.3 Secondary Objectives

Assess perceived effect of Amara on other gastrointestinal symptoms using validated, patient related outcome measurements (reflux disease questionnaire, IBS Symptom Severity Score).

Assess effect of Amara on (i) visceral sensitivity and (ii) gastric emptying (¹³C-breath test) in patients with functional dyspepsia with validated 400ml Liquid Nottingham Test Meal. Repeat testing will also allow an assessment of reproducibility to be obtained (iii) In a subset of 20 consecutive patients, gastric electrical activity will be measured using the non-invasive Gastric Alimetry System (high-resolution gastric mapping / electro-gastrography) with concurrent heart rate monitoring.

Participants will be asked also to rate their overall satisfaction with Amara and the number that request an additional prescription of Amara for the period after the study will be documented, as an indication of perceived effectiveness.

Additionally, factors that predict the outcome of Amara treatment in functional dyspepsia will be assessed. These factors will include (i) age (ii) sex (iii) severity of dyspeptic symptoms (iv) presence of other gastrointestinal symptoms (v) presence of psychological comorbidity (vi) presence of heightened visceral sensitivity after ingestion of the NTM (vii) abnormal gastric emptying during ¹³C gastric emptying test (viii) compliance with study procedures.

Additionally, the Lüscher Colour Test will be acquired. This non-verbal, non-written test was developed to provide insights into personality and psychological state. This could be of interest in patients with disorders of brain-gut interaction that may not admit to the role of central factors in their illness. Reproducibility of LCT will be documented by repeating the test at Study visit #1 and #2. Correlation with dyspeptic symptoms, psychological or physiological state will be assessed.

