5. STUDY OUTCOMES

5.1 **Primary Outcome**

The primary outcome will be the perceived change of dyspeptic symptoms assessed by the Leuven Dyspepsia Questionnaire (LDQ) between visit 1 (off treatment) and 3 (after treatment). The questionnaire contains 3 domains/questions which related to: a) The inability to finish a meal due to early satiety b) The feeling of food lying heavily in the stomach c) Feeling bloated in the stomach. The questionnaire is presented to the patients in the form of three questions which define five grades of severity (0-4), and which are supported by pictograms expressing the associated severity. Higher total scores indicate more severe dyspeptic symptoms. For each subscale 0 normal, 1 mild dyspepsia; 2, moderate dyspepsia; 3, severe dyspepsia; 4, very severe dyspepsia. The questionnaire is to be evaluated on a daily basis and the mean of the values of the three symptoms is proposed to represent the severity of that day. A weekly score can be calculated from the daily scores and is currently proposed for the primary use of the scale.(21)

The LDQ has been developed using standard methods, including focus group interviews and cognitive debriefing interviews.(21) The further validation of the score was undertaken with the means of interventional studies, evaluating the response of this questionnaire to prokinetic and neuromodulatory medications. The LDQ has shown to be a good rating scale to be used as a severity indicator of dyspepsia and can be given to the same patient in subsequent sessions to track the change in symptoms. A minimally clinically important difference has also been determined. The results of this validation work have been published in peer reviewed journals.(22, 23)

The Leuven Postprandial Distress Scale, which is supported by the European Medicines Agency, is a sensitive and reliable patient-reported outcome instrument to assess symptoms in the functional dyspepsia/postprandial distress syndrome. Based on this information, the LDQ variable will be the main result to verify whether the test medication in this trial is efficacious. In this open-label study in which placebo and treatment effects are summed we expect a moderate to large >60% reduction in mean symptom burden as measured by the LDQ (results will be shown as mean \pm SD).

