9.3.2 Study visits

On the second visit, patients will complete a combined assessment of gastric motor and sensory function off treatment with the Nottingham Test Meal, with gastric emptying documented by ¹³C-Breath Testing. On completion of the test, the test substance will be provided to the patient with instructions on how and when to take the Amara. An appointment will be made 4-6 weeks after this appointment for the third and final visit. Based on this, the start day for the intervention will also be determined.

During the 4-week intervention, 10-20 drops of Amara will be taken prior to every meal. Patients will document their symptoms every day using a mobile application. Adverse events can also be recorded. Paper forms are available if required. A reminder will be sent to complete this electronic form every day at 21:00.

Shortly before the third study visit participants receive an e-mail with a questionnaire link. All questionnaires will be completed again. If it is noted during the visit that the questionnaires has not been filled in, this can be done in the waiting room or during the visit. The patient will complete a combined assessment of gastric motor and sensory function on Amara treatment with the Nottingham Test Meal, with gastric emptying documented by ¹³C-Breath Testing. On completion of the test, in addition to the PROM, the patient will be asked about their subjective assessment of the intervention, whether ongoing treatment is desired and whether they would recommend the treatment to other patients with functional dyspepsia. Additionally, compliance with study procedures will be assessed (bottle(s) of Amara will be weighed). At the end of the study, patients are reimbursed a lump sum of 50 Swiss francs for expenses (gas, parking fee, train ticket etc.). More can be provided if an invoice supported by receipts is sent to the principal investigator.

In a subset of 20 consecutive patients, gastric electrical activity will be measured before, during and after ingestion of the Nottingham Test Meal on the second and third study visit using the non-invasive Gastric Alimetry System (high-resolution gastric mapping / electro-gastrography). Concurrent heart rate monitoring will provide an assessment of cardiovagal tone / autonomic nervous function.

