11.4.2 Primary Analysis

In the intention to treat analysis, all patients who have completed study questionnaires at baseline and after four-weeks of treatment will be included. Following covariates will be included in multivariate models: age, gender, dyspepsia symptom severity (LDQ), other gastrointestinal symptoms, psychological state and gastric function (sensitivity, emptying) at baseline.

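### Gastric function 'at baseline' is scheduled 2-4 weeks after the LDQ change starts, so drug-free run-in improvement can make low visceral sensitivity look predictive of response to Amara

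*Protocol*

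**What the plan says.** **The covariates.** Protocol 11.4.2 (primary) and 11.4.3 (per protocol) include age, gender, LDQ severity and "other gastrointestinal symptoms, psychological state and gastric function (sensitivity, emptying) at baseline". Section 11.4.1 lists the same variables in its text on subgroups.

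**The purpose.** Section 4.3 lists "presence of heightened visceral sensitivity after ingestion of the NTM" among the factors that may predict the outcome of treatment. Section 4.1 gives the aim: "This additional information should provide insight into which patients benefit the most from the treatment with Amara".

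**The LDQ.** Section 5.1 defines the change "between visit 1 (off treatment) and 3 (after treatment". The Study Schedule row "Primary Outcome Measure: LDQ total score" is ticked at visits 1 and 3 only.

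**Gastric function.** The row "Physiological Measurement (13C BT, HRV)" is ticked at visits 2 and 3 only. Section 9.3.2 agrees: "On the second visit, patients will complete a combined assessment of gastric motor and sensory function off treatment". The time estimate in 6.1 counts two emptying studies.

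**Text that conflicts with this timing.**
- The synopsis (Statistical Considerations) places baseline after the run-in.
- Section 9.2 has three LDQ assessments, with baseline separate from screening. Section 11.5 arguably makes the same distinction.
- Section 6.1 has the emptying study done *again* at visit 2, and the synopsis summary mentions gastric function testing just before it introduces the run-in. Both hint at a visit 1 test.

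**The concern.** A baseline predictor should be measured no later than the point from which the outcome is counted. Here the LDQ severity covariate comes from visit 1 and the gastric covariate from visit 2, yet both carry the label baseline.

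The protocol itself expects symptoms to move in between. Section 3.5 introduces the run-in because patients tend to present when symptoms are worse than usual. Visceral sensitivity is rated from sensations and symptoms during the test meal, so it may plausibly follow how the patient feels that day. A patient who improves spontaneously in the run-in would then rate the meal lower at visit 2 and also show a larger visit 1 to visit 3 fall. The visit 1 score cannot correct for this because it does not contain the run-in change.

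At stake is the objective in 4.1 and 4.3. Improvement without drug could be reported as a marker of who benefits from Amara. The limitations text in 6.1 describes this predictor analysis as relatively less sensitive to non-specific effects, yet here drug-free change can enter it directly.

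**Working it through.** **1. Share of the outcome interval before the covariate.** Visit 2 is 2-4 weeks after visit 1, and 9.3.2 puts visit 3 at 4-6 weeks after visit 2. The share runs from 2/(2+6) = 25% to 4/(4+4) = 50%.

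**2. Null model.** The protocol gives no variances or correlations, so every input here is assumed.
- LDQ at visit k is L_k = T + s_k + e_k. T is the stable level (variance 0.5), s_k the fluctuating state (variance 0.5, correlation ρ between successive visits) and e_k error (variance 0.3).
- Sensitivity S2 has variance 1 and correlation r with the true visit 2 level T + s_2.
- Every patient gets the same benefit, so sensitivity plays no role in response.
- The planned form regresses L1 - L3 on L1 and S2, n = 60.

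**3. Closed form, ignoring the entry threshold.** Given L1, the coefficient of S2 for the fall is minus its coefficient for L3.
- Cov(S2,L1) = Cov(S2,L3) = r(0.5 + 0.5ρ), and Cov(L1,L3) = 0.5 + 0.5ρ².
- Cov(S2,L3 | L1) = r(0.5 + 0.5ρ)[1 - (0.5 + 0.5ρ²)/1.3]. This is zero only if r = 0.
- With ρ = 0.6 and r = 0.4: 0.32 × (1 - 0.68/1.3) = 0.153.
- Var(L3 | L1) = 1.3 - 0.68²/1.3 = 0.944, and Var(S2 | L1) = 1 - 0.32²/1.3 = 0.921.
- Partial correlation = 0.153/√(0.944 × 0.921) = 0.164.
- Noncentrality = 0.164 × √57/√(1 - 0.164²) = 1.25, which gives p<=0.05 in about 23% of trials.
- The same steps give about 9% at r = 0.2 and 51% at r = 0.6.

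The coefficient for the fall is negative, so less sensitive patients appear to do better.

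**4. Simulation of the same model** (entry requires visit 1 LDQ above the mean; ρ = 0.3 or 0.6). Share of null trials in which S2 reaches p<=0.05:

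| Model, adjusted for its starting LDQ | no link | r = 0.2 | r = 0.4 | r = 0.6 |
|---|---|---|---|---|
| Start at visit 1 | 5% | 8-10% | 21-24% | 43-54% |

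Across r = 0.4 to 0.6, starting from a single visit 2 LDQ gives 7-17%, and starting from the mean of the last run-in week gives 5-6%.

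**5. A second simulation with other assumptions** (LDQ >= 4 at entry, stable and state SD 1.2, error SD 0.6, ρ between 0.3 and 0.8, correlations with the recorded visit 2 LDQ):

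| Link between sensitivity and symptoms | Start visit 1, adjusted | Start visit 2, adjusted |
|---|---|---|
| Stable and current, correlation about 0.55 | 49-58% | 7-16% |
| Stable and current, 0.33 | 22% | 7% |
| Current fluctuation only, 0.43 | 16% | 12% |
| Stable level only, 0.37 | 55% | 38% |
| None | 5% | 5% |

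In the 0.55 scenarios, regressing only the drug-free visit 1 to visit 2 change on visit 1 LDQ and S2 gives a significant S2 in 76-99% of runs. That points to the run-in as the source. In the stable-only scenario, measuring sensitivity at visit 1 still gives 54%, so timing explains little there.

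**6. Unadjusted regressions** (second simulation). The visit 1 to 3 change is significant in 6-12% of runs across the linked scenarios. An unadjusted visit 2 to 3 change is worse in most of them, up to 53%.

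**The case against.** **The baseline may be visit 2 for both variables.** The synopsis and 9.2 support that, and it would remove the mismatch. But 5.1, 4.2 and the schedule say visit 1, and 11.4.3 compares with scores at study begin. Nothing ties the two variables to the same visit, so an analyst who follows the schedule gets the mismatch.

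**Gastric function may also be tested at visit 1.** The wording in 6.1 and the synopsis allows this. The schedule, 9.3.2 and the count of two studies make visit 2 the better reading, but not an undisputed one.

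**The effect is conditional.** This stands. The documents give no correlation between test-meal sensitivity and symptoms. At 0.2 the excess over 5% is small, and with no link there is none.

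**Realignment does not fully cure it.** This also stands. If sensitivity follows stable symptom level, false prediction remains at about 10-26% with a weekly mean and 14-35% with a single visit 2 LDQ, for correlations 0.4-0.6.

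**The analyses are exploratory.** Sections 11.1 and 11.4 say so, and no significance will be claimed. That limits the severity. A coefficient pointing the wrong way can still mislead the later trial that this study is meant to inform.

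**It could be left to a later analysis plan.** Section 6.2.3 says the statistical analysis plan is in the protocol, and the protocol already fixes covariates, outcome interval and visits.

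**Conclusion.** The timing mismatch is real on the schedule, 5.1 and 9.3.2, and other passages contradict it. In the models adjusted for visit 1 LDQ, it can make low visceral sensitivity look predictive of response to Amara. The rates are about 8-10%, 21-24% and 43-54% of null trials at assumed correlations of 0.2, 0.4 and 0.6. These rest on assumed variances and on sensitivity following current symptoms.

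Three stronger readings are not supported:
- A reader might infer that the artefact is bound to occur. It needs a link for which the protocol gives no figure.
- A reader might extend it to gastric emptying. The mechanism concerns symptom ratings, and no such case is shown for the breath test.
- A reader might take it as a flaw in the primary test. That test compares LDQ scores without these covariates, so it is unaffected by this point.

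This is a worthwhile, inexpensive improvement to the exploratory predictor analyses.

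**What to change.** - In 11.4.1 to 11.4.3, state that every model or subgroup containing gastric function takes visit 3 LDQ as outcome, adjusted for the LDQ at the end of the run-in. That score also serves as the severity covariate.
- Take this score from the visit 2 baseline LDQ named in 9.2, and add it to the schedule. If the daily app records the LDQ items, use the mean of the last run-in week instead. The protocol says only that the app records the presence and severity of dyspeptic symptoms, so this must be confirmed first.
- Do not use an unadjusted visit 2 to visit 3 change.
- Reconcile the synopsis (summary and Statistical Considerations), the Study Schedule, 5.1, 6.1, 9.2 and 9.3.2 to one baseline visit.
- Report a sensitivity finding with the caveat that stable symptom level can still produce it.

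**Cost.** Wording, plus at most one three-item questionnaire at visit 2. If the primary test keeps its visit 1 start, the predictor models will begin from a different score, and this should be stated.

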11.4.3 Secondary Analyses

In the per protocol analysis (after four weeks), only patients who have taken at least half of the study medication will be included. Comparisons will be made between scores at study begin and scores after four weeks of treatment. Following covariates will be included in multivariate models: age, gender, dyspepsia symptom severity (LDQ), other gastrointestinal symptoms, psychological state and gastric function (sensitivity, emptying) at baseline.

11.4.4 Interim analyses

No interim analyses are planned.

11.4.5 Safety analysis

The side effects will be analysed with descriptive statistics as percentage of total (%) for categorical variables.

11.4.6 Deviation(s) from the original statistical plan

Any deviations from the original statistical plan will be justified and reported as appropriate.

11.5 Handling of missing data and drop-outs

Participants who filled out only the screening and/or only the first questionnaire (baseline) will be defined as dropouts. These dropouts will be replaced.

12. QUALITY ASSURANCE AND CONTROL

The Sponsor-Investigator is responsible for implementing and maintaining quality assurance and quality control systems with written SOPs. Every work step will be carried out and recorded accordingly.

Before the beginning of the study the PI will hold a proper training for all involved study personnel. Additionally, the staff will receive written documents concerning the study from the PI.

12.1 Data handling and record keeping / archiving

12.1.1 Case Report Forms

The electronic Case Report Form (eCRF, or paper equivalent if required) will comprise the participant's number, the standardised questionnaires LDQ, RDQ, IBS-SSS, HADS, PHQ, ICS, as well as sociodemographic and health-related data (Prüfbogen: Patientendaten, Gesundeheitsfragebogen), collected during screening. Additionally, outcomes of the physiological investigations detailing gastric function will be transferred in electronic form from the FAN Fischer ¹³C Breath Analysis device to the eCRF. The Lüscher Colour Test is not validated for use on electronic media. This information will be collected and analysed manually.

Prüfbogen (13-C Atemtest) and Prüfbogen (Checkliste) will be used as paper version. In exceptional cases, Prüfbogen (Patientendaten and Gesundheitsfragebogen) can also be completed on paper.

The participants will be identifiable in the eCRF/CRF neither by name nor by initials and nor by date of birth.

Once completed, data will be entered into REDCap. Any data from paper forms will be entered using the double data entry method. The data transfer from paper into the eCRF will be done at the Clinic Arlesheim. Only persons involved in the study are allowed to make eCRF entries. It will be assured that any authorised person making a CRF entry can be identified by name.

12.1.2 Specification of source documents

The ICF and the SAE standard form are found to be source data. Data collected through questionnaires in the CRF should also be considered being source data. Furthermore, any data from the clinical information system InesKis will be transferred to REDCap and be considered source data.

12.1.3. Record keeping / archiving

All study data (electronic or on paper) will be archived for a minimum of 10 years after the study termination or premature termination of the clinical trial. Data on paper will be stored in a lockable cabinet in the research department of the Clinic Arlesheim. Digital data will be kept on the internal of the server of Clinic Arlesheim, protected by a password and archived for a minimum of 10 years.

12.2 Data management

12.2.1 Data Management System

An eCRF will be prepared at the Clinic Arlesheim by the Research Group of [name]. med. [name] (Department of Gastroenterology, Clinic Arlesheim) with the REDCap software, a browser-based research data base. It is a widely used software in the academic research community. REDCap offers daily backups, basic support, and an audit trail feature for even more security.

12.2.2 Data security, access and back-up

REDCap creates automatic back-ups by the REDCap Team. Additionally, manual back-ups will be made by [name]. med. [name] and stored password-protected on the local server of the Clinic Arlesheim.

12.2.3 Analysis and archiving

REDCap provides automated export procedures for seamless data downloads to statistical analysis software. Data export files will be stored password-protected on the local server of the Clinic Arlesheim. Data analysis will be archived at Clinic Arlesheim for a minimum of 10 years.

12.2.4 Electronic and central data validation

REDCap provides real-time data validation, integrity checks, and other mechanisms for ensuring data quality (e.g., double data entry). Data validation ensures that correct data type is being entered and the value is within the expected range. Commercial statistical analysis software has built-in data validation mechanisms as well.

12.3 Monitoring

[name] will be responsible for the verification of the documentation for completeness and topicality (TMF), checking the data for completeness and plausibility, source data verification and the preparation of the monitoring plan and the monitoring report. All source data and documents are accessible to the monitor and all possible questions will be answered during monitoring (see Monitoring Plan).

12.4 Audits and Inspections

Study documentation and the source data/documents are accessible to auditors/inspectors (also CEC) and questions will be answered during inspections. All involved parties will keep the participant data strictly confidential. The inspector is independent of any person involved in the study.

During the audit, the following points are checked, among others:

- Performance of the study according to the study plan,
- Validity of the data,
- Quality of the study according to GCP guidelines.

After each inspection, the investigator receives a confirmation from the person responsible for the inspection. This confirmation is kept at the study centre in the research department.

